Any noticeable increase in significant postoperative complications would lead us to stop the study early however specific numbers will likely depend on the type of adverse event. For instance if 3 hips require surgical irrigations that would be a significant increase. However 3 surgical wounds that have significant erythema would not be a significant increase. We will have to remain aware of the status of these patients and be willing to be cautious if any noticeable increase in adverse events beyond what is expected occurs.

Adverse events will be graded on a 1-5 grading scale in line with the NIH adverse outcomes grading. Most relevant to our study will be adverse outcomes related to allergic reactions although any adverse outcome will be applied.

Grade 1 Mild AE, no intervention required

Grade 2 Moderate AE, local or noninvasive intervention required

Grade 3 Severe AE, invasive or hospitalization may be required

Grade 4 Life-threatening or disabling AE, urgent intervention may be required

Grade 5 Death due to AE

Grade 1 –Transient allergic reaction, such as itching, mild pain

2 – Localized rash or erythema, skin damage

3 – Full body urticarial, edema, excessive bleeding

4 – Bronchospasm, hypotension

5 – Death due to adverse event

If a significant number of adverse events occur we will discontinue the study immediately. Given the very low likelihood of adverse events related to this study we will have a low threshold to discontinue the study. Therefore, if 3 cases (This would then be 3% of the final number of participants) of serious adverse events (greater than grade 3) this will result in discontinuation of the study. This threshold was set due to the reported rate of allergic reaction and adverse events of this product being less than 1%. If 3% of patients are experiencing severe effects, than this would be over 3 times the expected percentage. This may be due to chance because of our low number of subjects. But given the severity and the possibility that this increase may be due to our specific institutions care routine, specific device, or other problems associated with our care it is reasonable to set this low threshold.

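### The three-case stopping rule counts only events above grade 3, so it leaves out the grade the plan itself labels Severe

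*Combined protocol and SAP*

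**What the plan says.** Section A.7.4 grades adverse events from 1 to 5. It defines "Grade 3 Severe AE, invasive or hospitalization may be required" and gives as grade 3 examples "Full body urticarial, edema, excessive bleeding". Grade 4 is life-threatening or disabling (examples: bronchospasm, hypotension) and grade 5 is death. Allergic reactions are named as the most relevant outcomes, "although any adverse outcome will be applied".

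The numeric rule then discontinues the study "if 3 cases (This would then be 3% of the final number of participants) of serious adverse events (greater than grade 3". Three reasons are given:

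- The team states that "we will have a low threshold to discontinue the study".
- The benchmark is the "reported rate of allergic reaction and adverse events of this product being less than 1" percent.
- "If 3% of patients are experiencing severe effects, than this would be over 3 times the expected percentage".

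The plan adds that "this increase may be due to our specific institutions care routine, specific device, or other problems associated with our care", which is its reason for caution even if the excess might be chance.

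Earlier in A.7.4, three hips needing surgical irrigation are given as an example of a significant increase in complications. Section A.7.5 says there is no data and safety monitoring board, and A.4.3 says the study is open-label.

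**The concern.** On a five-point integer scale, a cut-off above grade 3 leaves grades 4 and 5. The one grade labelled Severe is therefore outside the count, while the rule is justified by severe effects and by a wish to stop early. A threshold that counts only life-threatening or fatal events is a high bar on severity, whatever the number of cases.

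With no monitoring board, the investigators apply the rule themselves, and it is the only criterion in A.7.4 that ties a case count to a grade. If it omits the events it was set for, the formal part of the safety plan does not do what its rationale says.

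A secondary point concerns the benchmark. A rate reported for the product is compared with a percentage of all participants, but the product goes to only one of two equal arms.

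**Working it through.** **Inputs**

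- Three cases, grade above 3; benchmark below 1% (A.7.4).
- 90 recruited so that 80 complete, 40 funded for the device (A.8.4); 1:1 allocation (A.4.3). The device arm is therefore 40, or 90/2 = 45.
- No rate of grade 3 or higher events appears in the documents. All such rates below are assumptions.

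**1. The plan's own figure.** 3/90 = 3.33%, which rounds to the stated 3%, and 3.33%/1% = 3.3, which matches the stated multiple. 3/80 = 3.75% would round to 4%. The figure is therefore a both-arms figure based on 90 recruited.

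**2. The grade cut, side by side**

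| Event | Grade on the plan's scale | Counted as written? | Counted at grade 3 or higher? |
|---|---|---|---|
| Full-body urticaria, edema, excessive bleeding | 3 | No | Yes |
| Surgical irrigation (invasive) | 3, by the plan's definition | No | Yes |
| Bronchospasm, hypotension | 4 | Yes | Yes |
| Death | 5 | Yes | Yes |

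The irrigation row matters because A.7.4 itself treats three irrigations as a significant increase, yet the graded rule would score them as zero.

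**3. The benchmark among patients who wear the product.** If all three cases were on the device: 3/45 = 6.7% and 3/40 = 7.5%. Divided by 1%, that is 6.7 to 7.5 times the benchmark, about twice the multiple stated.

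**4. Chance of reaching three cases if grade 3 counts and the dressing has no effect.** With the same rate p in both arms,

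P(X ≥ 3) = 1 − (1−p)^n − n·p·(1−p)^(n−1) − [n(n−1)/2]·p²·(1−p)^(n−2).

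Example, n = 90, p = 0.01: 1 − 0.4047 − 0.3679 − 0.1654 = 0.062.

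| Assumed rate, grade 3 or higher | n = 80 | n = 90 |
|---|---|---|
| 0.5% | 0.8% | 1.1% |
| 1% | 4.7% | 6.2% |
| 2% | 22% | 27% |
| 3% | 43% | 51% |
| 5% | 77% | 83% |

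**5. How much the cut-off matters.** The same formula applies to the rule as written, with p multiplied by an assumed share of these events that are grade 4 or 5. At a 3% rate of grade 3 or higher events (n = 80 / n = 90):

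| Assumed share grade 4-5 | As written | Grade 3 or higher |
|---|---|---|
| 10% | 0.2% / 0.3% | 43% / 51% |
| 25% | 2.3% / 3.1% | 43% / 51% |
| 50% | 12% / 15% | 43% / 51% |

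The two readings give very different rules, so the wording has to settle which one applies.

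**The case against.** The strongest reply is that the text can be read coherently as it stands. The sentence about severe effects cites no grade, and life-threatening events and deaths are severe too. The low threshold may refer to the number of cases and not to the grade. The cut may even be deliberate: grade 3 includes edema, bleeding and hospitalization, any adverse outcome is in scope, and counting these after hip replacement could stop the trial for reasons unrelated to the dressing. This stands in part. It rules out calling the text a flat contradiction, and it makes the cost of the change real. It does not explain why the word the plan assigns to grade 3 carries the rationale, or why three irrigations are alarming in one paragraph and uncounted in another.

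A second reply is that other stops exist. A.7.4 would halt the project for any concern about patients' short- or long-term safety, for a noticeable rise in significant postoperative complications, for a significant percentage of treatment-group patients with unanticipated events, or for a significant number of adverse events. None has a grade limit, and three cases of full-body urticaria would plausibly engage several. A.6.11 also discontinues a device that causes serious allergies, and A.7.2 requires disclosure to the IRB. A reader might infer from the rule that grade 3 events go unprotected; the documents do not support that. These routes, however, depend on judgement or act on single patients, and they do not repair the graded rule.

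A reader might also infer from the benchmark mismatch that control-arm cases should not count. The documents do not support that either. The plan states an all-participant denominator and gives reasons that reach beyond the device to its care routine, so a trial-wide count is coherent. Correcting the comparison leaves the trigger unchanged.

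**Conclusion.** The concern holds as a flaw in the formal safety rule. As written, three out of three grade 3 cases go uncounted, and stopping for them rests on discretion. The documents do not show whether the authors meant grade 3 or higher, but the label, the stated rationale and the irrigation example all point that way.

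The benchmark mismatch is real but secondary: 3.3% of all participants would be 6.7-7.5% of device patients if every case fell in that arm.

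The grade finding and the proportions rest on the text alone. The stopping probabilities rest on assumed event rates, equal in both arms, and on independent patients. The rule should be corrected; the primary comparison of ASEPSIS scores at one week does not depend on it.

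**What to change.** In A.7.4:

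1. Change the cut-off to grade 3 or higher, and keep the count of three cases across both arms.
2. Reword the rationale so that 3 of 90 (3.3%) is not set against the product's rate as if every participant wore the device. Either drop the comparison or add that three device-arm cases would be 6.7% of 45 or 7.5% of 40.
3. State beside the rule the expected background rate of grade 3 or higher events after primary hip replacement in this setting, so that the chance of stopping without any device effect is visible.

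The edit is only wording, but it makes a stop more likely, including from ordinary postoperative events in either arm. With no device effect that chance is about 1-6% at an assumed background rate of 0.5-1%, and 43-51% at 3%. If the expected rate proves to be near the upper figure, the team should accept that chance knowingly when it adopts the rule. If grades 4 and 5 only were intended, the plan should say so and give a rationale that matches.

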#### A.7.5. Will this study involve a data and safety monitoring board or committee?

No

### A.8. Data analysis

#### A.8.1. Summarize the statistical analysis strategy for each specific aim.

Our primary goal is to test the difference between two independent groups at one week post op. Our feasible total sample size is 80 subjects. The progression of the ASEPSIS score over the six week post op recovery period will not be rectilinear. All patients are expected to be infection free with very low ASEPSIS scores immediately following the operation and are likely to be fully healed at six weeks. Attempting to model the timecourse of the ASEPSIS score with splines or multiple dummy variables and including all potential covariates would require considerable degrees of freedom and model tweaking based on intermediate assessments of model fit. Such a model would likely be too saturated to yield meaningfully narrow standard errors and holds considerable danger for overfitting. This modeling process does have some value for exploratory purposes, and we will employ it as such, but it will not be appropriate for confirmatory hypothesis testing. Instead, we note that the timepoint when differences in wound healing are most pronounced is after one week. Because subjects will be randomized to the two arms, we can consider the relevant population to be balanced on their covariates. The null hypothesis is simply that the treatments do not differ in ASEPSIS score at one week post op. Thus, we have a two independent groups t-test as a valid test

of our a-priori hypothesis.

A biostatistician ([name], NC TRACS) has been recruited and will provide the statistical computations and interpretive analyses required for the exploratory model-based analyses of the data. Estimates of effect magnitude, confidence intervals and sensitivity analyses will augment the exploratory modeling that will be conducted.

**A.8.2. What are the practical objectives of the study? Examples: pilot study to obtain data for a grant proposal, train junior investigators, create a registry, develop new assay methods, pilot-test procedures, evaluate feasibility, generate hypotheses, estimate parameters, test hypotheses.**

To determine the statistical difference in wound healing of patients treated with a standard dressing compared to the PREVENA dressing. We plan on publishing these results at completion of the study. We are unable to determine a difference in infection rate due to the small sample size, however the use of the ASEPSIS score allows us to identify differences in wound healing in this small study size.

**A.8.3. If this is a pilot study, please describe the future study and say how its study design, aims, sample size, and methods differ from the pilot study you are proposing.**

No Answer Provided

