## Part A. Questions Common to All Studies

### ▪ A.1. Background and Rationale

A.1.1. Provide a summary of the background and rationale for this study (i.e., why is the study needed?). If a complete background and literature review are in an accompanying grant application or other type of proposal, only provide a brief summary here. If there is no proposal, provide a more extensive background and literature review, including references.

Periprosthetic joint infections are a devastating complication due to their difficulty in treating, burden on the system, and patient morbidity and occurs in approximately 0.5% to 3% of primary total joint arthroplasties.[1–4] Revision total knee has both a detrimental physical and economic burden. Patients require treatment with intravenous antibiotics, multiple surgeries, and prolonged hospital courses. The clinical outcome of revision surgery for infection is also worse compared to other reasons for revision.[5] Periprosthetic infections also place a significant burden on hospitals. Increased blood loss, complications, and operative time lead to higher total hospital costs, longer hospital stays and increased outpatient visits. Revision arthroplasty compared to aseptic revision can cost more than \$60,000 more.[4] The cost of revision total joint arthroplasty is expected to be 1.6 billion in 2020.[6]

Periprosthetic infections can be related to a number of different factors both patient and environmental. Patient factors such as rheumatologic disease and obesity increase the risk of infection.[7–9] There is also evidence that surgical factors can increase a patient's risk. Time in the operating room, increased traffic, and protective clothing can also impact a patient's chance of developing a SSI.[10,11] Postoperative wound dressings have also been targeted as a means for reducing infection risk. Standard dressings generally consist of sterile absorptive dressings over the incision. Changes in dressing duration and type have yielded varying results. Recently, the use of Negative Pressure Wound Therapy (NPWT) has been investigated for the use on postoperative clean wounds.[12–18]

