#### Exclusion Criteria:

- age less than 18 y/o

- Total hip arthroplasty for fracture

- Revision or conversion total hip arthroplasty

- inability to personally consent to participation due to cognitive impairment, intoxication or sedation

- multiple surgical procedures

- Patients taking immune modulating medication(prednisone, methotrexate, anakinra, etc...)

- skin hypersensitivity to acrylic adhesive or silver.

- Inability to care for dressing due to physical or mental incapacitation

A.3.2. Justify any exclusion based on race, gender or ethnicity

Individuals will have equal opportunity to participate in the study regardless of gender, race and ethnicity.

A.3.3. Will pregnant women or women who become pregnant be excluded?

No

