Post Op Dressing	Staples over surgical incision, NPWT dressing
POD2	Dressing removed, staples remain in place, New sterile NPWT dressing placed

	NPWT dressing removed and sterile island dressing placed
1 Week Post Op	*Wound evaluated
2 Weeks Post Op	Island dressing removed and staples removed, no dressing placed *Wound evaluated

The evaluations to be recorded, and the occasions of evaluation, are detailed in **Table 1a** and **Table 1b**.

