**Table 1a. Measurements Recorded: Patient Profile Data**

Domain	Name of Variable	Description of the Variable	When Recorded
Identifiers	patient_ID	unique patient ID for this study	All occasions
	date	Date of each occasion	All occasions
	treatment_group	Treatment regimen assigned	Enrollment
Patient Factors	age	age in years	Enrollment
	gender	sex( male, female)	Enrollment
	allergies	list of allergies	Enrollment
	medical_history	medical history	Enrollment
	side	Side( left, right)	Enrollment
	co-morbidities	List of co-morbidities	Enrollment
Compliance	adherence	Self-reported adherence to protocol	All visits

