**A.8.4. Provide a compelling justification for the proposed sample size in terms of the likelihood of achieving each aim.**

Over the course of the study period, there will be a finite number of possible enrolled subjects. We expect to enroll a total target sample size of  $N = 80$  eligible subjects. Our funding will provide for 40 patients to undergo the new treatment plan with 40 standard dressing subjects as a comparison. We anticipate that about 10 subjects will have incomplete data due to compliance, drop-out, and other causes. This will result in a recruitment of up to 90 subjects in order to result in 80 subjects completing the trial.

Our primary goal is to test the difference between two independent groups at a specific time point (namely, one week post op). We can think of this as a two independent groups t-test. With  $n_1=40$  vs  $n_2=40$ , we will have 80% power to reject the null if the difference between the means of the two conditions were 0.63 standard deviations apart (and with greater power if the differences were bigger). Any difference of less than 0.63 SDs would be seen as not clinically significant. Small differences in the score of 1-2 points would fall within this and can be attributed to observer differences and would likely not be sensitive for detecting any risk for surgical infection.

The experimental dressing is expected to have benefit by reducing wound healing characteristics related to complications (ASEPSIS score) and subsequently reducing postoperative infections. There is an extremely low rate of infections in primary total hip arthroplasty surgeries and infection cannot be measured with this limited population (0.5% to 3.0% of the population). Adverse secondary events also have a low incidence and our study is not designed or powered to identify a statistically significant difference in these events, although such events will be recorded and examined for exploratory purposes. The ASEPSIS score allows a lower sample size that is within our reach to detect changes and will be used to identify infection risk.

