**Data Collection.** Study data will be recorded at the point of care using data collection instruments provided by the study team. Paper forms will be stored in a designated folder securely maintained at the point of care and will be retrieved by the study team on a daily basis. The subjects' medical records will be reviewed to obtain study data and the patient characteristics at admission (e.g., age, sex, race, BMI). The medical record data will be recorded on a patient-specific CRF. Data collection will adhere to precise written instructions and will be monitored to insure adherence to the protocol.

**Data Entry.** All data entered into the database from the CRFs will be verified by comparing the original CRFs to the values in the database.

**Data Editing.** The P.I. will be responsible for reviewing data-monitoring results and investigating questions raised (i.e., "queries") about remarkable or questionable data values.

**Database Documentation.** The names of the variables and their valid ranges or categorical values will be listed in a "data book". Documentation will also include an index of computer programs and an index of reports. All programming for statistical computation will include comments providing internal documentation.

**Pilot Testing of Operations.** All aspects of data management and project operation will be pilot tested prior to the commencement of the study in order to verify adequacy of the methods, materials and systems prepared. Every clinical study collects such pilot data -either intentionally prior to commencement of the study, or unintentionally after recruitment has begun.

**Risk of Deductive Disclosure.** We will minimize the risk of unauthorized persons using the database to figure out a subject's identity and responses.

(1) The database will comprise two separate files: a TRACKING FILE (containing sensitive patient identifiers such as name, birthdate, date and time of admission to the ER, and Subject\_ID) and a de-identified RESEARCH FILE containing non-sensitive data such as Subject\_ID, age, treatment assignment, ASEPSIS data, etc. Both database files contain Study\_ID. This allows the two sets of information to be linked together if necessary, but prevents linkage as long as the two files are kept safely separated.

(2) The database will be secured on encrypted storage media to guard against hacking or other unauthorized access. Paper forms will be stored in locked locations.

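### Does the one-week primary t-test need a prespecified BMI term because randomisation balances covariates only on average?

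*Combined protocol and SAP*

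**What the plan says.** Section A.8.1 sets the primary comparison as the mean ASEPSIS score in two independent groups at one week. It gives two reasons for leaving covariates out. One is randomisation: "Because subjects will be randomized to the two arms, we can consider the relevant population to be balanced on their covariates". The other is the danger of overfitting a time-course model, since splines or dummy variables and "including all potential covariates would require considerable degrees of freedom and model tweaking based on intermediate assessments of model fit". The section keeps such modelling, but only as exploratory work that is not to be used for confirmatory testing. It does not list the covariates for that work.

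Section A.8.4 sizes the trial on the same test: "We can think of this as a two independent groups t-test", with 40 against 40 patients and 80% power at a difference of 0.63 SD.

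Four other places bear on BMI:

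- The background (A.1.1) states: "Patient factors such as rheumatologic disease and obesity increase the risk of infection".
- The exclusion criteria remove one group with altered immunity, beginning "Patients taking immune modulating medication(prednisone, methotrexate, anakinra, etc", and set no BMI limit.
- Section A.8.5, under Data Collection, gives BMI as one example of what is taken from the medical record: "patient characteristics at admission (e.g., age, sex, race, BMI".
- Section A.4.2 states "The evaluations to be recorded, and the occasions of evaluation, are detailed in" Tables 1a and 1b. The first of these, "Table 1a. Measurements Recorded: Patient Profile Data", has age, gender, allergies, medical history, side and co-morbidities, but not BMI.

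**The concern.** Three things make this look like a weakness. Randomisation balances covariates in expectation, not in each trial, so the sentence in A.8.1 can be read as claiming too much for a sample of 80. The overfitting argument is aimed at a saturated longitudinal model and does not reach a single baseline term at a single time point. And the plan itself names obesity as a risk factor for infection and expects to have BMI from the record.

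If BMI were clearly prognostic for the one-week score, leaving it out would give up some precision. If an adjusted estimate appeared later with covariates nobody had named, a reader could suspect that they were chosen after the results were seen.

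**Working it through.** **Inputs.** From A.8.4: 40 per arm, difference 0.63 SD, power 80%. From A.4.3: 1:1 allocation. Not in the documents: the significance level (assumed two-sided 5%), the correlation ρ between BMI and the one-week score (assumed 0 to 0.3), and the share of patients with missing BMI (assumed 0 to 10%).

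**1. The plan's own figure.** The noncentrality is 0.63 / √(2/40) = 0.63 / 0.2236 = 2.817. With 78 degrees of freedom the critical value is 1.991 and the power is 79.5%. The normal approximation gives 80.4%. The stated 80% reproduces.

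**2. Chance imbalance.** The standardised difference in any baseline covariate has SD √(2/40) = 0.224. The chance that it exceeds 0.3 in either direction is 2 × [1 − Φ(0.3 / 0.2236)] = 18%. This is real, but it does not bias the test. The between-patient variance in the t-test's standard error includes whatever BMI contributes to the score, so such imbalances are part of the 5% error rate.

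**3. Power with one BMI term.** Adjustment multiplies the residual variance by (1 − ρ²). Estimating the slope under chance imbalance multiplies the variance by 1 + 1/76 on average. The degrees of freedom fall to 77. The noncentrality is 0.63 / √[(1 − ρ²)(1 + 1/76)(2/40)].

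| Assumed ρ | Noncentrality | Power | Change from 79.5% |
|---|---|---|---|
| 0 | 2.799 | 78.9% | −0.5 point |
| 0.1 | 2.813 | 79.3% | −0.1 |
| 0.2 | 2.857 | 80.5% | +1.1 |
| 0.3 | 2.934 | 82.6% | +3.1 |

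Simulation of 20,000 trials per value gave −0.5, +1.2 and +2.9 points at ρ = 0, 0.2 and 0.3. The break-even can be seen almost by hand: (1 − ρ²)(77/76) = 1 gives ρ² = 1/77 = 0.013, and the lost degree of freedom barely moves it (ρ about 0.115). A gain of one full point needs ρ of about 0.20.

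**4. Can the documents place ρ on that scale?** No. The sentence in A.1.1 ties obesity to infection, not to a wound score at one week. Section A.8.4 says that infection cannot be measured in a sample of this size. Nothing in the plan says whether ρ lies above or below 0.115.

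**5. Missing BMI.** The t-test needs no BMI, so a missing value costs it nothing. With the term added and incomplete cases dropped, power at ρ = 0.2 is:

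| Missing BMI | Patients per arm | Power |
|---|---|---|
| 2% | 39.2 | 79.7% |
| 5% | 38 | 78.4% |
| 10% | 36 | 76.1% |

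At 5% missing, the one-point gain has become a one-point loss (78.4% against 79.5%). Replacing missing values by the overall mean avoids this: at 10% missing, simulated power is 78.8%, 79.7% and 81.1% for ρ² of 0, 2 and 5%. But that is a remedy for a problem that the term itself would bring in.

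**6. Is the covariate choice open?** For the confirmatory test it is not: A.8.1 names one time point, one test and no covariates. Only the exploratory and sensitivity models lack a covariate list, and a BMI term in the primary model would not supply one.

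**The case for a change.** The best case for adjustment is that it is cheap. It takes a few lines of text and one degree of freedom, and costs at most about 0.5 point of power if BMI data are complete. The estimand stays a difference in means. The t-test could be kept as a supportive analysis, and naming one adjusted model beforehand would leave no doubt about how that estimate was chosen. A stated rule for missing BMI keeps every randomised patient, and simulated null rejection with mean imputation stayed between 4.8% and 5.2%.

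Much of this stands. Randomisation does balance only in expectation, the overfitting argument does not rule out one term, and adjustment would be a respectable choice. But none of it shows that the planned test is wrong or that the replacement is better here. BMI appears only as an example in a list. Age, sex and co-morbidities are firmly in Table 1a and could be argued for equally. The power figures also assume normal errors and a linear BMI effect, whereas ASEPSIS is a bounded sum of category points with 5- or 10-point additions for treatment events, and many low scores are likely. A gain this small need not carry over to such a score.

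Two minor points survive. Table 1a and the Data Collection text do not match on BMI, nor on race, which is also missing from the table. And the exploratory covariates could be named. Both are matters of housekeeping; A.8.5 already foresees a data book listing the variables. Neither alters the confirmatory result.

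**Conclusion.** The concern does not hold. The unadjusted t-test is a valid confirmatory analysis under randomisation, it is prespecified without covariates, and its stated power reproduces at 79.5% to 80.4%. Adding BMI would change power by −0.5 to +3.1 points over assumed correlations of 0 to 0.3. The documents do not settle even the sign, and dropping patients with missing BMI could outweigh a gain of one point. These figures assume a two-sided 5% level, 40 evaluable patients per arm and the plan's own normal model. The conclusion does not hang on their exact values: it rests on the validity of the planned test, on its covariate choice being fixed already, and on the absence of any evidence in the documents that BMI predicts the one-week score. Whether to adjust is a preference on which reasonable statisticians would differ, and the plan needs no change on this account.
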